#### Causal relationship of adverse event

The definition of an adverse reaction implies at least a reasonable possibility of a causal relationship between a suspected medicinal product and an adverse event. An adverse reaction, in contrast to an adverse event, is characterised by the fact that a causal relationship between a medicinal product and an occurrence is suspected.

Medical judgment should be used to determine the relationship, considering all relevant factors, including pattern of reaction, temporal relationship, de-challenge or re-challenge, confounding factors such as concomitant medication, concomitant diseases and relevant history.

Possibility high:	There is a reasonable causal relationship between JARDIANCE ® Tablets administered and the AE.
Possibility low:	It is probably/possibly that there is a reasonable causal relationship between JARDIANCE ® Tablets administered and the AE.
Unknown:	Cannot be judged because information is insufficient or contradictory.
Unrelated:	There is no reasonable causal relationship between JARDIANCE ® Tablets administered and the AE.

ADRs are defined that causal relationship is "Possibility high " or "Possibility low" or "Unknown".

Arguments that may suggest a **reasonable causal relationship** could be:

- The event is **consistent with the known pharmacology** of the drug
- The event is known to be caused by or **attributed to the drug class**.
- A **plausible time to onset of the event** relative to the time of drug exposure.
- Evidence that the **event is reproducible** when the drug is re-introduced
- **No medically sound alternative etiologies** that could explain the event (e.g. preexisting or concomitant diseases, or co-medications). The event is typically **drug-related and infrequent in the general population** not exposed to drugs (e.g. Stevens-Johnson syndrome).
- An indication of dose-response (i.e. greater effect size if the dose is increased, smaller effect size if dose is diminished).

Arguments that may suggest that there is **no reasonable possibility of a causal relationship** could be:

- No plausible time to onset of the event relative to the time of drug exposure is evident (e.g. pre-treatment cases, diagnosis of cancer or chronic disease within days/weeks of drug administration; an allergic reaction weeks after discontinuation of the drug concerned)
- Continuation of the event despite the withdrawal of the medication, taking into account the pharmacological properties of the compound (e.g. after 5 half-lives). Of note, this criterion may not be applicable to events whose time course is prolonged despite removing the original trigger. Additional arguments amongst those stated before, like alternative explanation (e.g. situations where other drugs or underlying diseases appear to provide a more likely explanation for the observed event than the drug concerned).

- Disappearance of the event even though the study drug treatment continues or remains unchanged.

Intensity of adverse event

The intensity of the AE should be judged based on the following:

Mild: Awareness of sign(s) or symptom(s) which is/are easily tolerated  
Moderate: Enough discomfort to cause interference with usual activity  
Severe: Incapacitating or causing inability to work or to perform usual activities

Pregnancy:

In rare cases, pregnancy might occur in a study. Once a patient has been enrolled into the PMS, after having taken JARDIANCE® Tablets, the investigator must report any drug exposure during pregnancy which occurred in a female patient or in a partner to a male patient to the Sponsor by means of Part A of the Pregnancy Monitoring Form. The outcome of the pregnancy associated with the drug exposure during pregnancy must be followed up and reported by means of Part B of the Pregnancy Monitoring Form.

In the absence of a reportable AE, only the Pregnancy Monitoring Form must be completed.

Expedited Reporting of AEs and Drug Exposure During Pregnancy

The following must be reported by the investigator to the Sponsor's unique entry point from first intake of JARDIANCE® Tablets at baseline visit and within 7 days (inclusive) after last intake:

Type of Report	Timeline
All SA DRs associated with the JARDIANCE ® Tablets	As soon as possible
All A Es with fatal outcome in patients exposed to JARDIANCE ® Tablets	As soon as possible
All non-serious ADRs associated with the JARDIANCE ® Tablets	As soon as possible
All pregnancy monitoring forms	As soon as possible

The same timelines apply if follow-up information becomes available for the respective events. In specific occasions the Investigator could inform the Sponsor upfront via telephone. This does not replace the requirement to complete the appropriate (e)CRF.

### Information required

For each reportable adverse event, the investigator should provide the information requested on the appropriate (e)CRF pages.

### Reporting of related Adverse Events associated with any other BI drug

The investigator is encouraged to report all adverse events related to any BI drug other than the JARDIANCE® Tablets according to the local regulatory requirements for spontaneous AE reporting at the investigator's discretion by using the locally established routes and AE report forms. The term AE includes drug exposure during pregnancy, and, regardless of whether an AE occurred or not, any abuse, off-label use, misuse, medication error, occupational exposure, lack of effect, and unexpected benefit.

#### **5.3.2 Reporting to health authorities**

Adverse event reporting to regulatory agencies will be done by the MAH according to local and international regulatory requirements.

#### **5.3.3 Assessment of safety laboratory parameters**

The laboratory tests will be performed when required by investigator.

Safety laboratory assessment will be performed according to local practice and if available the following parameters will be recorded in the eCRFs:

Haematology	Erythrocyte count (RBC), haemoglobin (Hb), haematocrit (Hct), Leukocyte counts (WBC) and platelet count.
Blood chemistry	HbA1c , Fasting plasma glucose, sodium (Na), potassium (K), chlorine (Cl), magnesium (Mg), calcium (Ca), phosphorus (P), creatinine (CRE), aspartate transaminase (AST, SGOT), alanine transaminase (ALT, SGPT), alkaline phosphatase (ALP), gamma-glutamyl-transferase ( $\gamma$ -GTP), albumin , lactic dehydrogenase (LDH), total bilirubin (T-BIL), blood urea nitrogen (BUN), total cholesterol (T-CHO), HDL cholesterol (HDL), LDL cholesterol (LDL), Triglycerides (TG), Amylase (AMY), Lipase (LIP) , uric acid (UA), 25-OH vitamin D, iPTH, ketone and creatine kinase (CK).
Urinalysis	Glucose, protein, urobilinogen, sediment, albumin, ketone and creatinine.

Enzymatic method:

$$\text{eGFR (mL/min/1.73 m}^2) = 194 \times \text{Creatinine (mg/dL)}^{-1.094} \times \text{Age}^{-0.287}$$

For female,  $\times 0.739$

Jaffe rate assay:

$$\text{eGFR (mL/min/1.73 m}^2) = 175 \times \text{Creatinine (mg/dL)}^{-1.154} \times \text{Age}^{-0.203}$$

For female,  $\times 0.742$

### 5.3.4 Electrocardiogram

If a resting 12-lead ECG will be performed by investigator's order during the PMS and the investigator should review the ECG data and record the results (abnormal Yes or No) in the eCRF.

### 5.3.5 Assessment of other safety parameters

#### Vital signs

Vital signs (usually blood pressure and pulse after 2 minutes supine rest) will be recorded at the screening visit and at the closest time points specified in the Flow Chart.

## **5.4 OTHER**

### **5.4.1 Other parameter**

#### **Demographics and history**

Demographics (gender, date of birth, indication, pregnancy status, height, body weight, waist circumference, hypersensitivity factor, alcohol habit, pre-treatment drug, diagnosed date of type 2 diabetes mellitus, smoking history, start date of administration)

Medical history (malignant tumor, cardiovascular/cerebrovascular disease (severity for cardiac failure for patients with past history of cardiac failure (NYHA classification)), urinary tract infection, genital infection, hypertension, osteoporosis, dyslipidaemia, goat/hyperuricaemia, others)

Concomitant disease (malignant tumor, cardiovascular/cerebrovascular disease (severity for cardiac failure for patients with past history of cardiac failure (NYHA classification)), urinary tract infection, genital infection, osteoporosis, others), presence or absence of diabetic concomitant diagnosis (neuropathy/nephropathy/retinopathy), degree of renal/hepatic functions at baseline, history of antidiabetic treatment (drug therapy, diet therapy)

### **5.4.2 Other assessment**

#### **Concomitant drugs and antidiabetic therapies**

Concomitant drugs and antidiabetic therapies present during PMS will be recorded in the CRF.

## **5.5 APPROPRIATENESS OF MEASUREMENTS**

All measurements performed during this PMS are widely used measurements to monitor safety and efficacy aspects of treatment of type 2 diabetes mellitus.

## **6. INVESTIGATIONAL PLAN**

### **6.1 VISIT SCHEDULE**

#### **Screening and run-in period(s)**

##### Before administration

The investigator will enter the following data of the patient into eCRF for registration. Preferably, registration should be executed within 14 days from the day of first administration of JARDIANCE® Tablets.

- Name of site, department and Investigator
- Patient ID, date of birth, gender, start date of administration, indication and serum creatinine.

#### **Treatment period(s)**

Patients will receive continuous daily treatment until the criteria for stopping medication are met according to the package insert.

During the treatment phase visits will be performed as planned if applicable and assessments will be documented within the nearest PMS visit.

#### **End of trial and follow-up period**

The visit at 156 weeks after starting JARDIANCE® Tablets treatment or the last visit before discontinuation will be the end of the PMS.

**6.2 DETAILS OF STUDY PROCEDURES AT SELECTED VISITS**

**6.2.1 Screening and run-in period(s)**

Screening Visit	
Screening Visit is before the first administration of JARDIANCE® Tablets	
Demographics	Gender, birth date, indication, pregnancy status, height, body weight, BMI (derived from weight and height), waist circumference, smoking history, duration of type 2 diabetes mellitus, grade of hepatic dysfunction and hypersensitivity factor.
Medical history / Concomitant disease	Document medical history and concomitant disease
Pre-treatment drug	Document start and stop date of each pre-treatment drug
Vital signs	Blood pressure and pulse rate.
ECG	Resting 12-lead ECG will be performed if applicable.
Laboratory tests	Haematology, Biochemistry, Urinalysis (see section 5.3.3 for minimum assessments).
Concomitant drugs and antidiabetic therapies	Document indication, start and stop date of each concomitant drugs and antidiabetic therapies.
Administration	Document dose and start date.

**6.2.2 Treatment period(s)**

Treatment period(s) 12, 26, 40, 52, 64, 78, 104 and 130 weeks after the start of treatment When stop the treatment, please complete the EOT visit instead.	
Vital signs	Blood pressure and pulse rate.
Body weight	Document body weight
Pregnancy status	Document when pregnancy is discovered.
ECG	Resting 12-lead ECG will be performed if applicable.
Laboratory tests	Haematology, Biochemistry, Urinalysis (see section 5.3.3 for minimum assessments).
Concomitant drugs and antidiabetic therapies	Document indication, start and stop date of each concomitant drugs and antidiabetic therapies.
Administration	Document dose, start and stop date and reason of termination.
Adverse events ██████████	Document details of any new AEs and obtain any new information about AEs ongoing at the last visit. ██████████ ██████████ ██████████

**6.2.3 End of trial and follow-up period**

End of trial EOT Complete this visit at 156 weeks after the start of treatment or at discontinuation.	
Vital signs	Blood pressure and pulse rate.
Body weight	Document body weight
Pregnancy status	Document when pregnancy is discovered.
ECG	Resting 12-lead ECG will be performed if applicable.
Laboratory tests	Haematology, Biochemistry, Urinalysis (see section 5.3.3 for minimum assessments).
Concomitant drugs and antidiabetic therapies	Document indication, start and stop date of each concomitant drugs and antidiabetic therapies.
Administration	Document dose, start and stop date and reason of termination.
Adverse events ██████████	Document details of any new AEs and obtain any new information about AEs ongoing at the last visit. ██████████ ██████████ ██████████

## 7. STATISTICAL METHODS AND DETERMINATION OF SAMPLE SIZE

### 7.1 STATISTICAL DESIGN - MODEL

This is a non-interventional, prospective and observational study to investigate the safety and efficacy of long-term use of JARDIANCE® Tablets in patients with type 2 diabetes mellitus.

### 7.2 NULL AND ALTERNATIVE HYPOTHESES

The analyses in this PMS are descriptive and exploratory by nature. No formal hypotheses tests will be made.

### 7.3 PLANNED ANALYSES

The safety evaluation will be performed on the “safety set” that will include all patients who have received treatment of JARDIANCE® Tablet at least one time except those who are found to have no observation after enrolment, invalid registration, or invalid contract with the site. The efficacy evaluation will be performed on the “efficacy set”, a subset of the safety set, which will include all patients in the “safety set” except those who have no available efficacy data and/or who do not suffer from type 2 diabetes mellitus.

[figure not shown]
#### 7.3.1 Primary analyses

In this PMS, the primary endpoint is the number of patient with ADRs. The details are given in Section [7.3.3](#)

#### 7.3.2 Secondary analyses

For change from baseline in HbA1c and FPG, descriptive statistics will be calculated with 95% confidence interval for the mean change from baseline.

A mixed model repeated measures analysis using all the available longitudinal observations during the observation period after the first administration of JARDIANCE® Tablets will be performed. Within-patient variability from all time points is assumed to have a particular variance-covariance structure, which is “compound symmetry.” Least square means will be computed at every time point and their respective standard error and 95% confidence interval estimate account for the estimated covariance parameters.

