**1245.94**

**Observational plan**

**c02153926-02**

Proprietary confidential information © 2015 Boehringer Ingelheim International GmbH or one or more of its affiliated companies

Name of company/Marketing Authorisation Holder: Boehringer Ingelheim		Tabulated Study Protocol	
Name of finished product: JARDIANCE® Tablets			
Name of active ingredient: Empagliflozin			
Protocol date: 10 APR 2015	Trial number: 1245.94		Revision date:
Criteria for efficacy:	Primary efficacy endpoint: None Secondary efficacy endpoint: Change from baseline in HbA1c and FPG to the last- observation on treatment.		
Criteria for safety:	Primary safety endpoint: Incidence of adverse drug reactions (ADRs)		
Statistical methods:	Descriptive statistics will be summarised for safety and efficacy. A mixed model repeated measures analysis will be performed for HbA1c over time.		

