### 3. DESCRIPTION OF DESIGN AND STUDY POPULATION

#### 3.1 OVERALL DESIGN AND PLAN

This PMS is a prospective study using a continuous investigation system. Patients with type 2 diabetes mellitus will be included in the surveillance. No specific criteria (e.g., demographics, baseline characteristics, concomitant drugs in use) are defined for patient enrolment.

[figure not shown]
Patients administered JARDIANCE® Tablets will be registered preferably within 14 days from the day of first administration. Patients will be observed for up to 156 weeks (approximately 36 months) after start of the treatment with JARDIANCE® Tablets or at premature discontinuation and dropout. Observations are made at the following time points: before first administration of JARDIANCE® Tablets (screening, this visit is defined as baseline) and 12, 26, 40, 52, 64, 78, 104, 130 and 156 weeks after the start of treatment, or at discontinuation.

There are 4 separate eCRFs for 0-12 (Book 1), 13- 52 (Book 2), 53- 104 (Book 3) and 105-156 weeks (Book 4).

[figure not shown]
At 12, 52, 104 and 156 weeks after the start of treatment or at discontinuation, data are to be transmitted immediately after entered into eCRF. In case of occurrence of any adverse events, data in corresponding observation period should be immediately entered into eCRF and transmitted.

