## **7.4 HANDLING OF MISSING DATA**

The REML based MMRM analysis will handle missing data for continuous efficacy endpoints for patients who discontinue the study treatment prematurely or whom corresponding assessments / measurements are not documented / available.

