## **7.6 DETERMINATION OF SAMPLE SIZE**

According to the request from the Japanese authority, this PMS will target to include 3,000 patients who complete a 3-year JARDIANCE® observation period. There is no target number of enrolment. For the 3,000 completer patients, an ADR with a true incidence of at least 0.10% (or 0.16%) will occur in at least one patient with a probability of 95% (or 99%).

In addition, according to the request from the Japanese authority, this PMS will target to include elderly patients, patients with renal dysfunction and hepatic dysfunction. The sample size for this patient subset was determined based on the following:

Elderly patients ( $\geq 75$  years)

Elderly patients were observed in 14.6% of the patients with type 2 diabetes mellitus based on the National Health and Nutrition Examination Survey (2007) [R13-5199]; it is estimated that approximately 400 ~ 500 elderly patients will be included in the 3,000 completer patients.

Based on this assumption, more than 100 elderly patients are highly likely to be enrolled in this PMS.

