4. CHANGES IN THE PLANNED ANALYSIS OF THE STUDY

There has been no change in the planned analysis from the statistical methods described in the NIS Protocol.

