6.2 IMPORTANT PROTOCOL VIOLATIONS

The following table defines the different categories of important PVs. The right-most column describes which PVs will be used to exclude patients from the different patient analysis sets. The final decision about which patients will be excluded from analysis sets will be taken during the course of the study and at report planning meetings before database lock at the latest.

Table 6.2: 1 Important protocol violations

Category/ Code	Description	Example/Comment	Method	Excluded from
A	Entrance criteria not met			
A1.1	No type 2 diabetes		Automated	Efficacy
A1.2	Patient received JARDIANCE [®] treatment before registration		Manual	All
B	Informed consent			
C	Trial medication and randomisation			
C1	Incorrect trial medication taken			
C1.1	No treatment with JARDIANCE [®]		Automated	All
E	Missing data			
E1	No baseline value	No available baseline value of HbA1c and FPG for efficacy analysis	Automated	Efficacy
G	Trial specific			
G1	Invalid registration			
G1.1	No patient visit after entry	Patient made no visit after the entry	Automated	All
G1.2	Multiple registration	Patient who were already registered in this trial or over the two trials(1245.94 and 1245.98) with another patient ID In this case, all data for the later patient will not be used.	Manual	All
G1.3	Registration rule not followed		Manual	All
G1.4	Patient started JARDIANCE [®] treatment out of registration period	Patients who started treatment after the end of registration period(31May2017) *Patients who started before contract period are not entered.	Automated	All
G1.5	Not continuous investigation		Manual	All

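### Compound symmetry is the only covariance given for the HbA1c MMRM over nine unequally spaced visits to week 156; late means and CIs rest on it

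*Protocol*

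**What the plan says.** The Protocol synopsis names the method: "A mixed model repeated measures analysis will be performed for HbA1c over time". Protocol 3.1 sets the observation times at "12, 26, 40, 52, 64, 78, 104, 130 and 156 weeks after the start of treatment, or at discontinuation", so there are nine post-baseline visits with gaps of 14, 14, 12, 12, 14, 26, 26 and 26 weeks.

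Protocol 7.3.2 gives one "variance-covariance structure, which is “compound symmetry" and derives the standard error and 95% CI of each visit's LS mean from the estimated covariance parameters. Protocol 7.4 adds: "The REML based MMRM analysis will handle missing data for continuous efficacy endpoints". Protocol 6.1 states that for patients who stop, "the last visit before discontinuation will be the end of the PMS", and SAP 6.6 allows no imputation for efficacy. The model alone therefore carries discontinuers to week 156.

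SAP 4 says: "There has been no change in the planned analysis from the statistical methods described in the NIS Protocol". The visible SAP 7.5.2 covers only the descriptive last-observation summary and does not mention the MMRM. Nowhere does the visible text give the fixed effects, say whether the response is HbA1c or its change, or name another covariance or a robust standard error. Parts of the SAP are redacted, so this absence is not proven.

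**The concern.** Compound symmetry (CS) is a strong assumption for three years of HbA1c, and two things follow if it is wrong.

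- **CI width.** One pooled variance serves all visits. Where the true variance at a visit is larger, its CI is too narrow; where smaller, too wide. If only the correlation decays, a visit-means model still gives about the right single-visit CI on complete data and a modestly narrow one with drop-out.
- **Bias.** A likelihood-based MMRM corrects for drop-out that depends on observed HbA1c only if the mean and covariance models are right. If CS holds, REML removes this bias. If it does not, the late LS means, where drop-out is heaviest, can be off. Sign and size depend strongly on the unstated fixed effects.

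At stake is the by-visit HbA1c curve, which is the long-term efficacy description. Protocol 7.3.4 also foresees interim results in publications.

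**Working it through.** **The plan's own figure.** Protocol 7.6 has no calculation for the MMRM. Its only one is the chance of at least one ADR in 3,000 completers, and it reproduces: 1 − (1 − 0.001)^3000 = 0.950 and 1 − (1 − 0.0016)^3000 = 0.992.

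**Inputs from the documents.** Nine visit weeks (Protocol 3.1); CS with REML (7.3.2, 7.4); about 3,000 completers (7.6).

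**Assumed inputs, because the documents give none.**
- Correlation 0.75·exp(−weeks/140): 0.68 at 14 weeks, 0.27 at 144 weeks.
- SD constant at 1.0, rising from 0.85 to 1.15, or falling from 1.15 to 0.85 between weeks 12 and 156; baseline has the week-12 SD.
- Week 12 seen in all; monotone drop-out with log-odds linear in the last HbA1c, slope 0.7 per point (range 0.3 to 1.0).
- 54% or 75% completing, with widths scaled to N = 6,000 or 4,000.

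Triplets below are constant/rising/falling SD.

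**Step 1: CI width, complete data, visit means.** The CS standard error is √(mean of the nine variances / n); the correct one is SD_t/√n. With SD linear in weeks, the mean variances are 1.000/0.966/1.053. The week-156 ratio, model over correct, is √1.000/1.00 = 1.00, √0.966/1.15 = 0.85 and √1.053/0.85 ≈ 1.2. With drop-out, simulation gives 0.91–0.96/0.78–0.82/1.06–1.14.

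With baseline-by-visit terms the ratios are 0.90/0.78/1.07 on complete data and 0.84–0.87/0.72–0.75/1.00–1.04 with drop-out. The constant-SD case is no longer 1.00 because baseline explains less as time passes: residual variance is 1 − 0.69² = 0.53 at week 12 and 1 − 0.25² = 0.94 at week 156.

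**Step 2: why bias arises.** For a patient seen only at week 12, CS carries a fraction ρ (its single fitted correlation) of the week-12 deviation to week 156. The correct fraction is 0.27 with constant SD, 0.27 × 1.15/0.85 = 0.37 with rising SD and 0.27 × 0.85/1.15 = 0.20 with falling SD. With constant SD, ρ lies between 0.27 and 0.68, so CS carries too much. Drop-outs have higher HbA1c, so the visit-means bias is upward, and largest with falling SD.

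**Step 3: week-156 bias under CS, slope 0.7 (400,000 simulated patients).**

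| Fixed effects | Completing | Constant | Rising | Falling |
|---|---|---|---|---|
| Visit means | 54% | 0.058 | 0.005 | 0.113 |
| Visit means | 75% | 0.027 | 0.003 | 0.054 |
| Baseline-by-visit | 54% | 0.002 | −0.030 | 0.034 |
| Baseline-by-visit | 75% | 0.001 | −0.014 | 0.016 |

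Unstructured covariance stays within 0.002 in both models. Over slopes 0.3 to 1.0, absolute CS bias is 0.001–0.148 (visit means) and 0.000–0.046 (baseline-by-visit). It exceeds the half-width of about 0.03 in 8 of 18 and 4 of 18 runs.

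**Step 4: half-widths at week 156, model against correct (54%, slope 0.7).** Visit means: 0.031 vs 0.034, 0.030 vs 0.038, 0.033 vs 0.030. Baseline-by-visit: 0.028 vs 0.033, 0.027 vs 0.038, 0.029 vs 0.029. The largest error is 0.038 − 0.027 = 0.011.

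**Step 5: week-156 coverage** (400 trials of 6,000, baseline-by-visit, 54%, slope 0.7). CS 91/47/32%; CS with sandwich SE 95/69/32%; unstructured 95/95/94%.

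**Step 6: other assumptions.**
- Slower decay (0.72 to 0.52), 54%: CS bias 0.028/−0.034/0.095 with visit means and −0.012/−0.040/0.017 with baseline-by-visit.
- A different set (visit means; correlations of CS 0.6, serial 0.85 per 13 weeks, or a mixture; SD ratio 1 or 1.5; slopes 0.5 and 1.0): −0.18 to +0.16 when CS is false, against −0.007 to +0.005 for unstructured. When CS is true, CS bias is at most 0.003.

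**Step 7: cost of unstructured if CS is true.** Half-width is 0.029 for both; coverage is 96.0% (CS) and 95.8% (unstructured). With about 60 patients at week 156, half-width is 0.19 for both, with coverage 95% against 94–95%. With about 30 patients, coverage is 96% against 88%.

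**The case against.** The case against is strongest on four points.

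1. **Redaction and assumed inputs.** A withheld SAP section may state the fixed effects or a fallback, and every SD, correlation and drop-out figure above is an assumption. Both stand as limits. But CS as the single structure, and its role as missing-data method, are in the visible Protocol, and SAP 4 declares no change.
2. **Most of the bias comes from the unstated fixed effects.** With constant SD and 54% completing, keeping CS and adding baseline-by-visit cuts bias from 0.058 to 0.002. This stands, and is why the covariance should not be changed alone. CS still leaves up to 0.046 when SD changes, and intervals that are too narrow in several cases.
3. **The figures can look worse than they are.** One of the 4 baseline-by-visit runs (−0.030) exceeds only the too-narrow model half-width of 0.027, not the correct 0.038. Coverage of 32% reflects a bias of 0.034 against a very small standard error. Fair on both counts.
4. **A baseline term may drop patients.** SAP Table 6.2: 1, item E1 ("No available baseline value of HbA1c and FPG for efficacy analysis") already removes patients with no baseline value from the efficacy set. The set definitions in Protocol 7.3 and SAP 6.3 do not repeat that condition, so they should be aligned. If E1 governs, the extra loss is only patients with baseline FPG but no baseline HbA1c.

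It is also true that no hypotheses are tested (Protocol 7.2), and that neither the primary ADR endpoint nor the last-observation summary uses this model.

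**Conclusion.** The concern holds, as a cheap improvement to a secondary descriptive analysis. CS is a restrictive sole assumption for nine visits over 156 weeks, and the visible text neither justifies it nor backs it up. Under the assumptions listed, the CI error is at most about 0.011 HbA1c points. Week-156 bias is often within the CI half-width but can exceed it several-fold in a visit-means model (0.148 against about 0.03). These values are illustrations, not bounds: sign and size change with the variance pattern, the drop-out mechanism and the fixed effects. If CS is true, or drop-out is unrelated to HbA1c, there is no material bias.

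**What to change.** In Protocol 7.3.2, and in the SAP section that describes the MMRM, state the response, fixed effects of visit, baseline HbA1c and baseline-by-visit, and an unstructured covariance (9 × 10/2 = 45 parameters, against about 3,000 completers).

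Do not change the covariance alone. If the response is change from baseline with visit means only, unstructured is more biased than CS in these runs (0.145/0.090/0.205 against 0.102/0.040/0.167; slope 0.7, 54% completing). With baseline-by-visit, HbA1c and its change give equivalent results.

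Set a fallback order for non-convergence, or for interim analyses where few patients have reached a late visit (for example fewer than about 60): heterogeneous Toeplitz, then CS with a sandwich SE. Toeplitz is a compromise, since it also ignores the unequal spacing. With baseline-by-visit its bias was −0.006/−0.008/−0.005, but with visit means it was 0.029/0.031/0.025. State that the sandwich SE repairs CI width but not drop-out bias.

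The cost is three or four sentences and no new data. The downsides are a longer specification, a small convergence risk, and weak unstructured CIs where a visit has only about 30 patients.
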